Movement Pattern Training in People with Intra-articular, Prearthritic Hip Disorders

NCT02913222

9-29-2016

RESEARCH STRATEGY

A. Significance: Effective treatment of PAHD needed to improve function and prevent or delay hip OA

Intra-articular, prearthritic hip disorders (PAHD) present as hip joint pain and loss of joint function with no radiographic evidence of osteoarthritis.^{18, 48} Associated diagnoses include femoroacetabular impingement, hip dysplasia, labral tears and chondral lesions. PAHD result in substantial hip dysfunction in young adults leading to significant limitations in walking, sitting and standing,^{10, 11, 44} thus restricting their ability to work or complete everyday tasks. Without proper management, PAHD may progress to hip osteoarthritis (OA),^{3, 24, 38, 49} a leading cause of reduced quality of life and loss of function for older people.

Current evidence in the treatment of PAHD is limited.^{2, 4, 41, 53} The preponderance of literature is related to surgical interventions and is primarily observational. There are no published clinical trials to compare surgical to nonsurgical treatment outcomes. Despite this evidence gap, the number of surgical procedures to treat PAHD has grown exponentially^{9, 39} before clinical trials have established the superiority of surgery over other treatment options. Rehabilitation provides a relatively inexpensive alternative to surgery, yet controversy exists regarding its effectiveness. Some authors believe rehabilitation can improve function in people with PAHD,^{13, 33} however others state that surgery is the best option.^{28, 30} This controversy may contribute to continued growth in the number of surgeries performed, with the potential for surgery to become standard treatment prior to rigorous investigation of treatment options. Our long term goal is to develop effective treatment strategies, surgical and nonsurgical, for people with PAHD that will improve function and prevent or delay the onset of OA.

Rehabilitation targeted at modifying abnormal movement patterns may lead to improved function and reduced pain in people with PAHD. Abnormal movement patterns, such as excessive hip adduction (Fig. 1), may create altered mechanical stresses on the hip joint structures, resulting in subsequent injury. Kumar et al³⁶ recently reported that excessive hip adduction motion during functional testing may be associated with articular cartilage damage in the hip joint. In our previous work investigating PAHD, we noted that increased hip adduction during a single leg squat was associated with lower patient-reported function. (See *Preliminary studies*). Given these novel findings, rehabilitation to optimize lower extremity movement patterns during functional tasks would be an appropriate approach for people with PAHD.

Movement pattern training (MPT) is an innovative rehabilitation approach with the goal to reduce stresses on the hip joint by optimizing the biomechanics of functional tasks. The key element of MPT is *task-specific instruction* to correct abnormal movement patterns during daily and fitness activities. In our previous study, we assessed the feasibility of using MPT in addition to hip strengthening for the treatment of PAHD.²¹ **After participating in treatment, people with PAHD were able to reduce hip adduction during functional tasks and this reduction was associated with improved patient-reported function (See *Preliminary studies*).** Surprisingly, hip muscle strength did not improve after treatment, nor was strength associated with functional improvement or hip adduction reduction, raising questions about the relationship among hip strength, hip-specific function and lower extremity movement patterns in people with PAHD. Although no studies have reported the use of MPT in patients with PAHD, similar approaches have been used in low back pain,^{27, 32, 50, 52} anterior cruciate ligament tear prevention,^{29, 47} and patellofemoral pain.⁴³ If determined to be effective in the rehabilitation of PAHD, MPT may also serve a role in injury prevention and post-surgical rehabilitation. Additionally, we believe MPT can be feasibly implemented into community practice with minimal training and equipment. We have successfully implemented MPT in our current clinical practice.

B. Innovation: Novel treatment using movement pattern training to improve function

The novel theoretical concept of the proposed study is that a person's movement pattern may contribute to the development and persistence of pain related to PAHD. The Physical Stress Theory⁴⁰ states that repetitive or prolonged stresses may result in tissue injury if the tissue's capacity to accept stress is exceeded. The Movement System Impairment Theory⁴⁶ builds upon the Physical Stress Theory by stating that

[figure not shown]

Figure 1. Static images representing hip motion during single leg squat. Hip adduction is represented as the angle between line (a) drawn perpendicular to the pelvis (dashed line) and line (b) bisecting the thigh. **A.** Abnormal movement pattern demonstrating excessive hip adduction **B.** Reduced hip adduction after MPT.

mechanical hip pain is the consequence of repeated use of *abnormal movement patterns* during daily activities. Abnormal movement patterns may create altered mechanical forces on joint structures, thus changing the location and magnitude of stress to specific joint tissues, such as the articular cartilage and acetabular labrum.⁴⁶ Repeated loading of hip joint with altered mechanical forces may contribute to cumulative tissue stress, micro-trauma, pain and potentially osteoarthritis.¹⁵ Until the abnormal movement pattern is modified, the hip pain may persist or recur. We have reported extensively on the Movement System Impairment Theory in people with low back pain.^{26, 27, 31, 32, 50, 51}

We will assess the effect of MPT on correcting abnormal movement patterns, reducing pain and improving function in people with PAHD. This *approach is innovative* by focusing treatment on modifying abnormal movement patterns that may contribute to altered stresses on the hip joint structures, instead of the traditional approach of focusing rehabilitation on isolated physical impairments, such as muscle weakness¹⁴ and limited joint flexibility.^{13, 14} Impairment-based treatment may improve the body's overall capacity, however may not improve hip biomechanics. For example, lower extremity strengthening exercises may increase the muscle's force production capability, however this increased force production capability may not result in improved quality of movement during daily tasks. In this proposal, we will perform a multicenter, feasibility RCT to compare the efficacy of our novel treatment strategy, MPT, to standard, impairment-based rehabilitation.

C. Approach

Overview of the team and the approach

In the future trial, we will need large, generalizable samples that would be difficult, if not impossible, to recruit at one site. Therefore two sites, Washington University and University of Pittsburgh, will participate in the feasibility RCT. Drs. [name] and [name] will serve as principal investigators (PI). The Steering Committee will include the PIs and Drs [name] and [name] (See *Project Leadership Plan*).

Washington University, Study Coordinating Center: The Study Coordinating Center ([name], Director) will oversee personnel training, protocol implementation, data collection and follow-up. [name] is an orthopedic physical therapist with a Master's of Science in Clinical Investigation. As part of her training (K23HD067343), she successfully completed an exploratory trial to assess the feasibility of MPT in the treatment of PAHD. Washington University provides substantial infrastructure to support this project (See *Facilities and Other Resources*). Our multidisciplinary hip group (See *letters [name], [name], [name], [name]*) has substantial expertise in PAHD and experience in participant recruitment for clinical research. The Data Coordinating Center ([name], director) will administer the study, perform scientific oversight, ensure quality control and perform data analysis.

University of Pittsburgh: The Physical Therapy – Clinical and Translational Research Center (PT-CTRC) ([name], Director) will oversee study implementation at the University of Pittsburgh site. [name] will also guide [name] in developing and implementing methods to optimize treatment fidelity among treatment providers. Methods he has used successfully in his previous RCTs will be used in the proposed study. [name] is an experienced investigator and recognized expert in OA,¹⁶ who has conducted multiple RCTs examining the effectiveness of rehabilitation related to lower extremity disorders.^{1, 17, 45} The PT-CTRC provides significant infrastructure to perform multicenter clinical trials including access to potential participants, facilities, equipment and support for new investigators (See *Facilities and Other Resources*).

[figure not shown]
Timeline: We have developed a Manual of Procedures to facilitate consistency in participant recruitment, protocol implementation and data collection across sites. We are developing training modules to optimize the treatment providers' adherence to study protocol. The study planning phase will include a pretrial meeting of the Steering Committee and onsite training of study personnel. Methods for the proposed study, described below, were optimized in the previous study, therefore we will initiate participant recruitment within one month of study start. Recruitment will proceed for 17 months (months 2-18) with the last follow-up being completed by month 21. The last 3 months will be used for data analysis and study close-out.

Preliminary studies supporting the approach

Aim 1: Participant adherence: Based on the previous study (K23), we are confident we will meet recruitment and retention goals of the project. In the study, we randomized 35 people with PAHD into an immediate treatment group (n=18) or a wait-list control group (n=17). The treatment group participated in 6 sessions of MPT. Overall retention rate was 91%; 2 in the treatment group and 1 in the wait-list group did not return after baseline testing. Treatment adherence was high; 15 of 16 who participated in treatment attended all supervised sessions and 1 attended 5 of 6 sessions. Additionally, 89% of those in the treatment group reported

completing their home program at least once per day. Using methods optimized in the previous study, we anticipate similar adherence in the proposed study.

Aim 2: Post-treatment improvement in outcomes: In our previous study (K23), we used patient-reported outcomes and 3D motion analysis to assess post-treatment improvement in function and lower extremity movement patterns respectively. We noted, with baseline assessment, that increased hip adduction motion during a single leg squat, may be associated with lower patient-reported function, quantified using the modified Harris Hip Score ($r = -0.28, P = 0.08$) (*unpublished data*). Compared to wait-list control, those who participated in MPT demonstrated improved post-treatment function²¹ (Fig. 2) that was associated with a reduction in hip adduction ($r = -0.60, p=0.001$) (Fig. 3). Additional preliminary data suggests these post-treatment improvements in function are maintained up to 12 months after treatment.²⁰ These preliminary results suggest that MPT may be an effective treatment approach for people with PAHD, however comparison to standard rehabilitation is needed.

Experimental approach

Participant Recruitment: 46 participants will be enrolled. To be enrolled, participants must 1) be 15-40 years old, 2) report deep hip joint or anterior groin pain, confirmed upon physical exam, 3) report pain $\geq 3/10$ and present ≥ 3 months and 4) demonstrate functional limitation with modified Harris Hip Score <90 . Exclusion criteria include 1) previous hip surgery, fracture, pelvic/hip infection, or pain due to high impact trauma, 2) inflammatory disease, e.g. rheumatoid arthritis, gout and 3) neurological involvement affecting balance.

General Procedures

Aim 1: Participant adherence and treatment fidelity: Participant adherence to treatment sessions will be documented by the treatment providers. Participants will complete daily logs of home program performance. To optimize retention, participants will be contacted at regular intervals by the site-specific research coordinator. Any barriers to study participation will be documented and addressed. To optimize treatment fidelity among study personnel, we will use training methods established by [name]. We also will use the treatment fidelity framework developed by the NIH's Behavioral Change Consortium.^{7,8} Treatment providers will be contacted monthly to identify barriers to treatment fidelity. Booster sessions to review key components of study protocol will be provided at months 9 and 15.

Aim 2: Post-treatment improvement in outcomes (Fig. 4): Informed consent will be obtained prior to testing. Participants will complete self-report questionnaires and participate in movement pattern assessment. Participants will then be randomized into 1 of 2 treatment groups, movement pattern training (MPT) or standard rehabilitation (Control). Both groups will participate in 10 supervised sessions and perform a home program

within a 12 week time frame. At 13 weeks after enrollment, participants will return for testing to assess post-treatment improvements in primary and secondary outcomes.

Specific Procedures (Aims 1 and 2)

Primary outcome – Function: At pre-treatment and post-treatment testing, participants will complete the Hip disability and Osteoarthritis Outcome Score (HOOS),⁴² a reliable and valid³⁴ hip-specific, patient reported outcome measure. Basic demographic, medical history and medication use will also be collected. (Appendix 1). All questionnaire responses will be collected and managed using Research Electronic Data Capture (REDCap, See *Facilities and Other Resources*) system hosted at Washington University. We will use the tailored design method of survey procedures, used in our previous study, to motivate participants to respond.¹²

Minimum important change (MIC) for HOOS subscales has not been established for patients undergoing non-surgical management for PAHD. Using values established for people who have undergone arthroscopic surgery,³⁴ the MIC values for HOOS subscales of ADL and Symptoms are 6 and 9 respectively. In our **preliminary work**, statistically significant differences exceeding MIC were found in HOOS ADL and Symptoms, with those participating in MPT demonstrating greater improvement at follow up compared to those in the wait-list group (Fig. 2).

Secondary outcome – Movement pattern: We will use a digital camera to acquire 2D hip motion while participants complete tasks of varying difficulty: step down, single leg squat, drop vertical jump. Markers will be placed on anatomical landmarks of the pelvis and thigh to assist with hip angle measurement. Previously published procedures²⁵ for camera placement and participant positioning will be used to optimize between-site data collection and reduce the effect of projection angles on the 2D measures. Participants will practice each movement prior to testing. We will then collect 3 trials of each movement. Commercially available software will be used to measure peak hip adduction motion. All measurements will be completed by trained personnel at Washington University, who will be blinded to treatment group.

In our **preliminary work**, we used 3D kinematic methods to quantify hip motion during the single leg squat. For the current study, we chose to use a 2D method that can be easily replicated with simple equipment in the clinical setting. To assess our ability to predict 3D peak hip adduction angle using our proposed 2D method, we used digital videos synchronized to the 3D kinematic data collection. Using data from 12 randomly selected participants, we found the correlation between 2D and 3D peak hip adduction to be high ($r = 0.85$, $P < 0.001$). Test-retest reliability of our 2D method is excellent ($ICC_{3,3} = 0.996$); standard error of measurement of 0.47° .

Randomization: Participants will be randomized to 1 of 2 treatment groups in a 1:1 ratio stratified by sex and HOOS Symptoms quartile (as determined from the preliminary data) within each site. Within each stratum, participants will be allocated using a variable block size so that the desired allocation ratio will be maintained at intervals throughout the recruitment process. Randomization sequences will be generated a priori using a formal probability model and will be elicited from the data capture system. Given the nature of the intervention, it is not possible to blind the treatment providers or participants to treatment assignment. Study personnel performing the assessments or the movement pattern measurements will be blinded to group assignment.

Treatment: Treatment for both groups will include 10 supervised sessions over 12 weeks. After randomization,

[figure not shown]

Figure 4. Study flow diagram. CONSORT flow diagram adapted. WU = Washington University; UP = University of Pittsburgh. Note: Using additional support from WU, 6 & 12 month data will be collected during and after the funding period to assess durability of post-treatment improvement.

scheduling for participants, the treating physical therapists will be trained and tested in standardized procedures for both treatment arms. Both treatment arms will include assessment of patient goals, patient education and instruction in a home program. Patient education will focus on patient-specific tasks, identified by the participant to be symptom-producing. Based on participant responses during our **preliminary work**, patient-specific tasks included work-related and fitness activities, such as running, cycling and swimming. Participant independence and adherence will be documented (Appendix 2).²² A brief description of the treatment approaches are provided below.

Movement pattern training (MPT) (Appendix 3): Focus will be on task-specific training to improve lower extremity movement patterns during basic functional tasks, such as sit to stand and stair negotiation, and reported patient-specific tasks. Patient education will include instruction in abnormal movement patterns and methods to optimize their movement pattern during each task. Exercises will include repeated practice of functional tasks using optimized movement patterns. Verbal cues and visual aids, such as a mirror, will be used to assist the participant. Based on the participant's performance, the difficulty of the task-specific activities will be progressed by varying the repetitions performed, increasing the load or changing the support surface. The home program will consist of repeated practice of tasks performed during supervised sessions.

Standard rehabilitation (Control) (Appendix 4): Focus will be on progressive lower extremity and trunk strengthening and lower extremity flexibility. Patient education will include instruction to modify intensity, frequency or duration of patient-specific tasks. Using current clinical practice guidelines¹⁴ and previous reports,^{6, 53} strengthening and flexibility exercises will be prescribed and progressed by varying the repetitions performed or increasing the load. The home program will include exercises performed during supervised sessions.

Post-treatment assessment: Participants will return for questionnaire completion and movement pattern assessment immediately after treatment. We will compare pre-treatment measures to post-treatment measures of both treatment groups to assess change in functional ability (HOOS) and movement patterns. Additionally, participants will complete a questionnaire developed to determine barriers to treatment adherence and to assess 1) treatment receipt, '*did the participant receive the treatment as intended*' and 2) treatment enactment, '*was the participant able to successfully implement their new skills*'.^{7, 8} To assess sustained effects of treatment, participants enrolled at the Washington University site will return for questionnaire completion and laboratory testing 1-2 years after treatment

Additional measures: We will collect additional measures, to assist in the future trial development. To assess the feasibility of using PROMIS, the NIH-funded Patient-Reported Outcomes Measurement Information System for people with PAHD, we will use the computer-adapted version of the physical function and mobility domains. Using previously reported methods,²³ we will assess hip muscle strength pre- and post-treatment. Finally, using additional funding from Washington University (See letter, [name]), participants will complete study questionnaires, electronically administered, 6 and 12 months after treatment to assess durability of post-treatment improvement.

Sample size considerations: With a sample size of 46 (23/group), the 95% confidence bounds (CBs) around our overall rates of adherence and retention will be between 78% and 96%, meaning that estimates will be within 9% of the true rate. The within site and within group estimates of adherence will be within 13% of the true rate. These calculations assume that the observed rates will be at least 90%, which is reasonable to expect based on our preliminary data. Aim 2 will estimate intervention effect sizes and as such, the study is not designed to generate definitive results. However, with at least 20 participants/group completing pre- and post-testing, the study will have 80% power to detect large effect sizes of 0.9 or above, with 95% CBs between 0.27 and 1.53. We note that preliminary data for the primary outcomes indicate that approximately 50% of the variance in change is explained by the pre-treatment value, and thus power and precision will be increased by including this covariate in the analyses.

We anticipate no problems enrolling sufficient participants for this feasibility study. We were able to enroll 3-5 participants per month during our previous study. To improve our likelihood of meeting recruitment goals, we have added the University of Pittsburgh site and established collaborations with additional healthcare providers in St. Louis. We have also removed the restriction from the previous study for body mass index (previously <30 kg/m² required for kinematic testing). Support from the Data Coordination Center ([name], Director) will assist in optimizing retention rate and patient follow-up. Additionally, we will provide compensation of \$25/hour to offset travel effort and costs related to the testing sessions and treatment will be provided at no charge.

Statistical Analysis: The primary data analyses for Aim 1 will be descriptive, and include reporting the rate of recruitment, screening, and enrollment for all potential participants considered for the study; and reasons for non-enrollment. Adherence, retention, and fidelity rates will be categorized using the specified thresholds and reported with 95% CBs. Uncategorized rates will be compared between sites and groups by Wilcoxon's test. Aim 2 will generate estimates of effect sizes. We will report change between pre-and post-treatment with 95% CBs. Inferential analyses will compare the change in response to treatment using analysis of covariance (ANCOVA) where change is the dependent variable and the pre-treatment value is the covariate. Accounting for variation in pre-treatment function will increase the precision of the between-group comparisons and also adjust the treatment effect estimates for possible imbalances between groups. If statistical assumptions are not satisfied, transformations will be explored or nonparametric covariance analyses³⁵ will be used.

Data Management and Quality Control: Study data will be electronically captured using the REDCap system hosted in a limited access data center managed by the Data Coordinating Center. Additional quality control programs will verify that study identification numbers are accurately labeled, evaluate consistency over time, and check for incomplete or overdue data. Routine reporting will monitor recruitment and retention, overall quality, and protocol deviations. Throughout the study, standardization of procedures across sites will be ensured by dynamic training and monitoring that includes site visits and remote auditing.

Limitations and Alternative Approaches: We have proposed this feasibility RCT to assess the ability to perform a multicenter RCT. Multicenter studies have unique challenges, however we believe this is a strength of our study by allowing us to achieve large, generalizable samples. We have developed a team with individual strengths that, when brought together, will optimize our ability to successfully complete this project and subsequent studies. Although a new investigator, [name] has demonstrated her capability to lead a project by completing an exploratory RCT (*manuscript in review*) during her K23 training grant. Drs. [name] and [name] are experienced investigators, with significant experience implementing multicenter studies. [name] is well-recognized for his clinical expertise in PAHD and has an established research agenda with the goal of improving patient outcomes through investigation of nonsurgical and surgical treatment strategies.

Given our preliminary data, we expect those receiving MPT will report improved function after treatment. It is possible those receiving the standard rehabilitation will report similar improvements. Although unexpected, this finding would be important to demonstrate that nonsurgical management may be an option for people with PAHD. Study data will then be used to guide the development of future improved treatment strategies. If we find similar improvements in both groups, it is likely some participants will respond favorably to the treatment approach they received, while others remain unchanged or possibly worsen. Secondary analysis of patient-specific factors and movement pattern assessment may identify subgroups of people with PAHD who would respond to different types of treatment.⁵

We did not include imaging in this study. Imaging would provide useful information about bony abnormalities^{19, 37} and structural disease associated with PAHD, however would be cost-prohibitive for this feasibility study. In our **preliminary work**, we did not find an association between patient-reported function and bony abnormalities. We therefore chose to focus on the abnormal movement pattern in this study. Imaging to assess bony abnormalities and structure disease will be included in the future, definitive trial.

Significance and future directions: Information from the current study regarding the participants' ability to adhere to treatment, the treatment providers' ability to adhere to the treatment protocol and effect size estimates will guide the future, large RCT. Should the feasibility study indicate that modifications are needed, these will be made prior to the large RCT. Feedback from study participants and the treatment providers will be used to improve participants adherence and treatment fidelity. The future RCT will include assessment of patient-reported function and movement patterns from the proposed study and bony abnormalities. A better understanding of the association among these factors and treatment prognosis will help us develop improved treatment strategies and to better match treatment to patients.

Intra-articular, prearthritic hip disorders result in significant limitations in the young adult and are likely precursors to osteoarthritis. MPT is an innovative treatment approach with the potential to optimize treatment outcomes, nonsurgical and surgical, for people with PAHD. Further, MPT may provide a strategy for injury prevention, particularly those injuries of insidious nature. Ultimately this work will lead to better overall outcomes, reduced healthcare cost and reduced patient burden.

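### No masking to visit and no reading order is specified for the hip-adduction videos, so the within-arm pre-to-post changes are open to reader expectation and reading drift

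*Combined protocol and SAP*

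**What the plan says.** The section Secondary outcome – Movement pattern describes 2D video of three tasks, with markers on pelvis and thigh and three trials of each task. On the reading itself it says: "Commercially available software will be used to measure peak hip adduction motion". Reading is central: "All measurements will be completed by trained personnel at Washington University, who will be blinded to treatment group". The Randomization section repeats the masking statement: "Study personnel performing the assessments or the movement pattern measurements will be blinded to group assignment". Both statements cover the arm only. No section mentions removing visit or date labels, the order in which clips are read, or whether one reader handles both of a participant's clips.

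Change over time is a planned result. Post-treatment assessment says: "We will compare pre-treatment measures to post-treatment measures of both treatment groups to assess change in functional ability (HOOS) and movement patterns". Statistical Analysis adds: "We will report change between pre-and post-treatment with 95% CBs". The inferential comparison is "analysis of covariance (ANCOVA) where change is the dependent variable and the pre-treatment value is the covariate".

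**The concern.** A person with software takes the angle from stored video, so some judgement in choosing the peak and placing the lines plausibly remains. The team has a directional expectation, at least for MPT: its preliminary work linked better function to reduced adduction, and Figure 1 illustrates reduced adduction after MPT. A reader who knows that a clip is post-treatment could lean that way without knowing the arm.

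Reading order raises a separate problem. Post-treatment testing comes 13 weeks after enrolment, and recruitment runs for 17 months. If clips are read as they arrive, any drift in reading practice between a participant's two clips is counted as change.

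Masking to arm removes neither error from the within-arm change, and a larger sample would not shrink either. The confidence bounds would be centred in the wrong place while looking as precise as before. Significance and future directions says that the effect size estimates will guide the larger trial and that movement patterns will be assessed there too, so the reading procedure may carry forward.

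**Working it through.** **Inputs from the documents.** Completers: "with at least 20 participants/group completing pre- and post-testing" (Sample size considerations). Reading repeatability: "standard error of measurement of 0.47" degrees, with an ICC of 0.996 (Secondary outcome – Movement pattern). These figures describe repeatability. They say nothing about a systematic shift tied to visit.

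**Assumed inputs.** The documents give no SD of change in hip adduction. I take 4 to 6 degrees and check 3 degrees as well. The shift *b* is a constant added to every post-treatment reading. I show 0.47 degrees (the stated standard error of measurement, used only as a yardstick), 1 degree and 2 degrees.

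**The plan's own Aim 2 figure.** The plan states 80% power at a standardized effect of 0.9 with 20 per group, and bounds of 0.27 to 1.53. I assume two-sided alpha of 0.05. Power is 81.2% by the normal approximation and 79.2% by the noncentral t with 38 df. The standard error is √(2/20) = 0.316, and 0.9 ± 2 × 0.316 gives 0.27 to 1.53. The figure reproduces and is not in dispute. Masking to visit would not change it.

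**Within-arm bounds under a shift.**

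- Half-width = t(0.975, 19) × SD/√20 = 2.093 × SD/4.472 = 0.468 SD. This is 1.87 degrees at SD 4 and 2.81 degrees at SD 6.
- Coverage = P(−2.093 < T < 2.093), where T is noncentral t with 19 df and noncentrality δ = *b*√20/SD.
- Example: *b* = 1 and SD = 4 give δ = 4.472/4 = 1.118 and coverage 0.814.

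| SD of change (assumed) | *b* = 0.47° | *b* = 1° | *b* = 2° |
|---|---|---|---|
| 4° | 92.1% | 81.4% | 43.5% |
| 5° | 93.2% | 86.4% | 60.3% |
| 6° | 93.7% | 89.1% | 70.6% |

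At SD 3 the three values are 89.8%, 70.6% and 19.3%. With *b* = 0, coverage is 95%.

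**Between-group estimate under the same shift.** Write change = intercept + (treatment effect × group) + (slope × baseline) + *b* + error. If *b* is the same in both arms, the intercept absorbs it, and the treatment estimate and its standard error do not change. A simulation of the planned ANCOVA agrees (4,000 runs per setting, 20 per group, baseline explaining 50% of the variance of change, *b* = 0, 0.3 and 0.5 SD of change). Bias in the treatment effect stayed within 0.01 SD, and the type I error was 4.9% to 5.8%. Since the algebra is exact, that spread is simulation noise.

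**The case against.** The strongest reply is that the plan is silent on visit and does not say that readers know it. Timeline mentions a Manual of Procedures covering data collection across sites. It is not among the documents and may already deal with file coding and reading order. This stands: a reader might infer that the measurers are unmasked to visit, but the documents support only that no such masking is specified.

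A second tempting inference is that the treatment comparison is biased. The documents do not support it. Readers are masked to arm, as stated twice, and a common shift cancels in the ANCOVA. One could argue that knowing the visit makes the arm easier to guess from a visibly coached movement. That is plausible but unquantified, and a coached movement stays visible after the label is removed.

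Other replies stand in part:

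- The expectation is clear for MPT but weaker for standard rehabilitation. The Innovation section itself doubts that strengthening improves movement quality, so a reader masked to arm has no sharp expectation for a given clip.
- Markers, standard camera placement, software and trained central readers limit discretion, though they do not exclude a systematic shift.
- Within-arm change has no control. Even with perfect reading it could not separate treatment from practice or natural course.
- The shift sizes are assumptions, and at 0.47 degrees the harm is slight.
- The outcome is secondary, in a 46-person feasibility trial that the plan describes as not definitive.

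These points lower the priority. They do not remove the gap, because the plan commits to reporting the within-arm changes with bounds.

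**Conclusion.** The point holds, limited to the within-arm pre-to-post changes in peak hip adduction. Reader masking is specified for treatment group only, with neither masking to visit nor a reading order, so those changes are open to reader expectation and drift.

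The size is unknown. With 20 completers per arm and an assumed SD of change of 4 to 6 degrees, coverage of the within-arm 95% bounds would be about 92–94% for a 0.47-degree shift, 81–89% for 1 degree and 44–71% for 2 degrees. These are conditional illustrations; nothing in the documents shows that a shift of any size occurs.

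The between-group estimate is largely unaffected as long as masking to arm holds and any shift is common to both arms. HOOS, which participants complete themselves, is not affected. This is a cheap improvement to a secondary outcome, not a threat to the trial's main results.

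**What to change.** In Secondary outcome – Movement pattern, replace the sentence on who measures the videos with:

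> Video files from both sites are coded and stripped of date, visit and group. Each participant's pre- and post-treatment clips are read by the same reader, in random order interleaved with other participants' clips, with the reader masked to visit and group; baseline clips of participants without a post-treatment clip are included in the same batches. Clips are checked for technical quality on receipt, without angle measurement.

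Interleaving matters because reading one participant's two clips side by side invites comparison and may reveal their order. The check on receipt keeps delayed reading from hiding camera or marker problems at either site. If the Manual of Procedures already requires this, it is enough to say so in the protocol.

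The cost is file coding and a randomized reading list. Readings must also wait until the post-treatment clip exists or the participant is lost. Reading is already centralized at one site, and batches can be read during recruitment as participants complete, so the work need not all fall in the last 3 months, which also serve for analysis and close-out. The number of readings, the sample size and the power do not change.
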